## **Methods:**

### **Study Design:**

Single-arm study involving five (5) subjects undergoing 6 90-minute sessions of Pulsed Electromagnetic Therapy. All patients received the same treatment. Harnesses were placed on the head, wrists, and ankles of the body to conduct the electromagnetic frequencies. Patients were encouraged to rest and relax whilst the therapy was conducted, as it does not require any tasks by the patient. Patients were required to complete a questionnaire before and after the trial. This questionnaire enquired about the different symptoms related to PTSD and Trauma, and asked patients to rate their symptoms on a scale. These questionnaires would form the foundation of the study's findings, as it would give a clear comparison of symptoms before and after the trial.

All aspects of the trial were exempt from a U.K. ethics committee board review because the trial was a non-invasive method of treatment, did not collect and tissue or fluid samples and the device is CE-marked and had been used in other trials previously approved and published on Clinical Trials.gov. Documents were provided on clinicaltrials.gov as evidence of this exemption.

All patients were from the inclusion criteria, and any patients exhibiting cases from our exclusion list were rejected from the pilot study. Patients were recruited through the National Centre for Electromagnetic Therapy social media pages, including Facebook, Instagram, and [www.ncet.co.uk](http://www.ncet.co.uk).

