## Results & Findings

### **Prior to the Trial**

Once participants had been screened and approved for clinical trial study, they were required to fill out a questionnaire that sought to establish the specific issues that they were experiencing due to PTSD and Trauma. These responses were weighted as an average and are provided below.

For clarification, a rating of one (1) on the scale indicates a very severe case of a specific symptom, five (5) means a frequent feeling of a symptom, and ten (10) indicates that the symptom is not experienced at all. A weighted average score has been chosen as a foundation for our results, to compare them more accurately before and after the trial. However, specific notes and observations shall be included where needed.

Statements were also used, whereupon a patient would respond with either Daily (3 or more times a week), Weekly (2 to 3 times a week), Monthly (3 to 4 times a month), or Rarely (Once every 3 months or longer).

Question	Average Score
Have you experienced or witnessed a life-changing event that caused intense fear, hopelessness or horror?	All patients recorded 'Yes'.
Have you experienced either repeating dreams, flashbacks, or intense physical/emotional stress that relate back to the	Daily – 1 Patient Monthly – 2 Patients Rarely – 2 Patients

traumatic event(s)?	
Do you avoid thoughts, feelings, actions, conversations, or people related to the event?	Daily – 1 Patient Weekly – 2 Patients Monthly – 1 Patient Rarely – 1 Patient
Have you felt detached or negative towards yourself or others since the traumatic event(s) happened?	Daily – 4 Patients Monthly – 1 Patient
Do you have problems sleeping?	Daily – 1 Patient Weekly – 2 Patients Rarely – 2 Patients
Do you become increasingly irritable, angry, or engage in self-destructive behaviour?	Daily – 1 Patient Monthly – 3 Patients Rarely – 1 Patient
How long have your symptoms persisted?	Longer Than Three Years – 3 Patients Longer Than A Year – 1 Patient 8-12 Months – 1 Patient
Do you experience heightened version of anxiety, sensitivity, or depression?	Daily – 3 Patients Weekly – 1 Patient Monthly – 1 Patient
Rate Your Quality of Life	Average Score: 6
Rate The Severity of Depression	Average Score: 6.4
Rate How Difficult It Is To Fall Asleep	Average Score: 5.6
Rate The Severity of Flashbacks Relating to a Traumatic Event	Average Score: 5
Rate The Severity of Headaches or 'Brain Fog'	Average Score: 4.6
Rate The Severity of Fatigue	Average Score: 5

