### After The Trial

Once the trial had been completed over the course of 3 weeks, patients were asked to complete the same questionnaire that was sent out prior to the clinical trial. In the table below, responses have been recorded as an average, with a percentage comparison of improvement or decline in symptoms.

Question	Average Score
Have you experienced or witnessed a life-changing event that caused intense fear, hopelessness or horror?	All patients recorded 'Yes'.
Rate Your Quality of Life	Average Score: 8 ( Improvement of >2 points )
Rate The Severity of Depression	Average Score: 6.4 ( No change )
Rate How Difficult It Is To Fall Asleep	Average Score: 8.2 ( Improvement of >2.6 points )
Rate The Severity of Flashbacks Relating to a Traumatic Event	Average Score: 7.4 ( Improvement of >2.4 points )
Rate The Severity of Headaches or 'Brain Fog'	Average Score: 6 ( Improvement of >1.4 points )
Rate The Severity of Fatigue	Average Score: 6.8 ( Improvement of >1.8 points )
Rate The Severity of Anger or Irritable Outbursts	Average Score: 7.4 ( Improvement of >2.6 points )

Rate How Difficult It Is To Complete Daily Tasks	Average Score: 7.4 ( Improvement of >1.6 points )
Rate The Severity of Your Anxiety	Average Score: 7 ( Improvement of >0.8 points )
Rate Your Level of Overall Happiness	Average Score: 8.2 ( Improvement of >2 points )
Rate Your Level of Satisfaction and Fulfilment In Life	Average Score: 7.8 ( Improvement of >2 points )

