## Discussion

Regarding nearly all the symptoms analysed in the clinical trial, there was a mild to significant improvement. The largest improvement of an average of 2.6 points was discovered in symptoms related to insomnia and anger outbursts. It can be hypothesised that due to increased rest and relaxation, patients were able to manage their negative emotions more efficiently.

Positive results were also found within the patients' own value of life. Large improvements were found in a patients' perception of overall happiness, satisfaction and fulfilment, as well as general quality of life. All these values increased by a score of 2 or more on average. It is evident that the PEMF treatment is beneficial in providing patients with a relaxing and calm therapy which in turn helps appreciation for quality of life, and motivation in facing daily tasks head on.

Physical symptoms were also improved using PEMF therapy. Issues relating to headaches, fatigue, and flashbacks were all reduced over the course of the trial. Patients reported feeling more relaxed, and physical pains has subsided (See 'Patient Four' below).

It is important to note that the only symptom that experienced no average change was depression. It can be postulated that this is due to depression being a more deep-rooted issue which was prevalent for an extended period prior to the clinical trial. It is promising to see that cases of depression were not worsened during the trial, indicating that PEMF therapy is able to improve symptoms related to depression (fatigue, insomnia, anger). Nonetheless, the lack of change in depression forms a consideration for future clinical trials (see 'Considerations').

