It is of the opinion of the National Centre of Electromagnetic Therapies that this clinical trial was a success in meeting its primary objective in improvement symptoms related to PTSD and Trauma through PEMF. The clinical trial has highlighted the many benefits of PEMF treatment. Nearly all studied symptoms improved for all patients during the trial, and there was no worsening of symptoms recorded. The evidence provided within this document attests to these conclusions.

Therefore, it is recommended that further clinical trials into the development of Pulsed Electromagnetic Therapy as treatment for symptoms of PTSD and Trauma should be conducted. It is our goal to conduct a similar study on a far larger scale, with more participants and a longer trial period. This conclusion has been reached due to the promising positive benefits of PEMF therapy shown through this clinical trial. The clinical trial also concludes that PEMF therapy is a beneficial, non-invasive alternative to prescription medication in relation to PTSD and Trauma. Whilst the results cannot claim to be representative of the entire U.K., the clinical trial has indicated that there are significant benefits to Bio-Resonance treatment and should therefore be studied further.

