## 1.2

Do you avoid thoughts, feelings, actions, conversations, or people related to the event?

[figure not shown]
5 responses

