## Survey After Clinical Trial

### 2.1

#### RATE YOUR QUALITY OF LIFE

[figure not shown]
5 responses

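### The conclusion that all patients improved and none worsened is not shown by the reported results, which are group averages with no after-trial result for six symptom-frequency questions

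*Combined protocol and SAP*

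**What the plan says.** Study Design describes a "Single-arm study involving five (5) subjects undergoing 6 90-minute sessions of Pulsed Electromagnetic Therapy". Patients filled in a questionnaire before and after treatment. The results section uses a scale from 1 (very severe) to 10 (symptom absent), so a higher score is better.

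- **Before** (Prior to the Trial): counts of daily, weekly, monthly or rare occurrence for six symptom questions, and averages for 11 rated items. The averages are called weighted, but no weights are given.
- **After** (After The Trial): it states that "patients were asked to complete the same questionnaire that was sent out prior to the clinical trial". The table below that sentence has the yes/no life-event question and averages for the same 11 rated items.
- **Discussion**: depression had no average change, and "cases of depression were not worsened during the trial".
- **Closing text of Reflections and Considerations**: "Nearly all studied symptoms improved for all patients during the trial, and there was no worsening of symptoms recorded", followed by "The evidence provided within this document attests to these conclusions". The same paragraph says that the primary objective was met.

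**The concern.** The Discussion mostly reports average changes. The closing text turns these into statements about every patient, and an average over five people can rise while some of them get worse. The closing text also speaks of no recorded worsening, although part of the before-trial questionnaire has no after-trial result at all.

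This sentence supports the claim of success on the primary objective. A reader would take from it that the treatment helped everyone and harmed no one's symptoms. The reported tables show something narrower: averages that rose on 10 of 11 rated items.

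**Working it through.** **1. The stated changes reproduce.** After minus before equals the stated change for all 11 items. Multiplying each average by five gives the patient totals below. All 22 averages are multiples of 0.2, which suggests equally weighted whole-number ratings, though the document does not say so.

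| Item | Before | After | Change | Total before | Total after | Change in total |
|---|---|---|---|---|---|---|
| Quality of life | 6 | 8 | 2 | 30 | 40 | +10 |
| Depression | 6.4 | 6.4 | 0 | 32 | 32 | 0 |
| Falling asleep | 5.6 | 8.2 | 2.6 | 28 | 41 | +13 |
| Flashbacks | 5 | 7.4 | 2.4 | 25 | 37 | +12 |
| Headaches | 4.6 | 6 | 1.4 | 23 | 30 | +7 |
| Fatigue | 5 | 6.8 | 1.8 | 25 | 34 | +9 |
| Anger | 4.8 | 7.4 | 2.6 | 24 | 37 | +13 |
| Daily tasks | 5.8 | 7.4 | 1.6 | 29 | 37 | +8 |
| Anxiety | 6.2 | 7 | 0.8 | 31 | 35 | +4 |
| Happiness | 6.2 | 8.2 | 2 | 31 | 41 | +10 |
| Satisfaction | 5.8 | 7.8 | 2 | 29 | 39 | +10 |

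**2. Depression.** Let d_i be patient i's change and w_i > 0 the same weight both times. The averages give Σ w_i d_i = 0. If no d_i is negative, every d_i must be 0. So either all five patients were exactly unchanged or at least one worsened. This needs no assumption about whole numbers, and the text does not say which case applies.

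**3. Anxiety.** The total rises by 4. With equally weighted whole-number ratings, improvement in all five would need a rise of at least 5 × 1 = 5, so at most four improved. With half-point ratings all five could have improved (for example 0.5 + 0.5 + 1 + 1 + 1 = 4).

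**4. What the averages cannot exclude.** Assume equally weighted whole-number ratings from 1 to 10. One patient can gain at most 9 points, and each who worsens loses at least 1.

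- Four worsened: the net change is at most 9 − 4 = +5. Only depression (0) and anxiety (+4) satisfy this.
- Three worsened: the net change is at most 2 × 9 − 3 = +15. Every item satisfies this, the largest being +13.

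An exhaustive search over all scores with these totals confirms the limits: 0 to 4 worsened on depression and anxiety, 0 to 3 on the other nine. The largest possible number improved is 4 on depression and anxiety, and 5 on the other nine.

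**5. Questions with no after-trial result.** These are dreams or flashbacks, avoidance, detachment, sleep problems, irritability, and heightened anxiety or depression. Leaving out the life-event and duration questions, the before-trial table has 6 + 11 = 17 symptom and wellbeing questions:

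- average improved: 10/17 = 59%
- average unchanged (depression): 1/17
- no after-trial result: 6/17 = 35%

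The illustrations show the same gap. Before-trial charts run from 1.1 to 1.20. Under "Survey After Clinical Trial" the charts run from 2.1 to 2.11 without a break, and all are rated items. The 20 − 11 = 9 charts with no counterpart are the six frequency questions, duration (1.6), anger outbursts (1.7) and medication efficacy (1.18).

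Two of the six have no rated item to stand in for them: "Do you avoid thoughts, feelings, actions, conversations, or people related to the event" and "Have you felt detached or negative towards yourself or others since the traumatic event(s) happened". Four of the five patients answered the second with daily before the trial.

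**The case against.** The strongest defence has four parts.

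- **No recorded average fell.** The results are recorded as averages, and 10 of 11 rising fits nearly all. This is true for the rated items at group level. It does not cover the words about all patients, or the frequency questions.
- **Patient-level evidence may lie elsewhere.** The text refers to individual patient statements, and the conclusion points to the whole document. The chart images and some patient statements were not available to this review and may narrow the uncertainty for some items. Separate before and after charts do not normally link one patient's two scores, however. For depression they could not settle the matter: five whole-number scores averaging 6.4 cannot all be equal, so even identical charts would allow patients to have exchanged scores.
- **The limits are extremes.** Four worsening on anxiety would need the fifth patient to gain at least 4 + 4 = 8 points. That is right, and the limits say only what the averages fail to exclude. Also, four of the six frequency questions have a related rated item, so the full gap is in avoidance and detachment.
- **Unequal weights with rounding** could hide a small rise in depression with nobody worse. This is a narrow possibility, and the 0.2 multiples make unequal weights unlikely.

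The closing text is also labelled as opinion and calls for larger trials. That softens its tone, but the sentence still says that the document's evidence attests to it.

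**Conclusion.** The concern holds and should be fixed. Within the tables and text available, the claims that all patients improved and none worsened are unsupported. They are not disproved, and nothing here shows that any patient worsened.

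Confidence is high on depression, where the unchanged average fits the claim only if all five patients scored exactly the same twice (given constant weights and setting rounding aside), and on the six questions without an after-trial result. The statement that at most four improved on anxiety, and the ranges of possible worsening, depend on equally weighted whole-number ratings. If the frequency questions count as studied symptoms, improvement in nearly all of them is not shown even at group level. For avoidance and detachment, no reported result allows a check.

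**What to change.** 1. If before and after forms can be linked by patient, tabulate for each of the 11 rated items the number improved, unchanged and worsened, with the mean paired change and its SD (a 95% CI is optional). Keep the wording about all patients and no worsening, here and in the Discussion on depression, only where that table shows it.
2. Report the six frequency questions as before and after counts, which needs no linking. If they were not asked again, say so and correct the statement that the questionnaire was the same.
3. If the forms cannot be linked, restate the conclusion: average scores improved on 10 of 11 rated items and average depression was unchanged. If the frequency questions remain unreported, add that they have no after-trial result, including avoidance and detachment.
4. Clerical: remove the greater-than signs before the changes, which are exact differences, and either give the weights or call the averages unweighted.

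With five patients this is a small re-tabulation, or a wording change if linking is impossible; the document does not say whether it is possible. No new data are needed. The price is a less favourable conclusion.

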## Study Summary

Title	Pulsed ElectroMagnetic Field (PEMF) therapy in Treating Post-Traumatic Stress Disorder (PTSD) & Trauma
Methodology	Single arm observing treatment intervention; no control, no placebo/sham
Study Duration	Estimated duration for the main protocol (the start and end of the treatment programme) is approximately 3 weeks
Study Centre(s)	Private clinic in Bristol, U.K.
Objectives	
Primary Objective: To evaluate the efficacy of Artificial Intelligence (AI) guided software rendering PEMF treatment to treat PTSD & Trauma
 
Secondary Objective: To evaluate the feasibility of AI implementation in drastically reducing the time required to train PEMF therapists, thereby allowing faster adoption of PEMF therapy into mainstream practice through use by other licensed/regulated/trained healthcare professionals such as talking therapists, nurses, doctors, social workers, and carers

Number of Actual Participants	5
Diagnosis and Main Inclusion Criteria	
Inclusion Criteria:
 
 
• Aged 18 or over
 
• Have been diagnosed with PTSD or Trauma
 
• Have been experiencing on-going, continuous symptoms of PTSD or Trauma for at least the past 6 months
 
• Can attend 6 sessions lasting 90 minutes over 3 weeks
 
• Consent and Compliance with all requirements of clinical trial, including dissemination of results, with anonymity of identity provided
 
 
Exclusion Criteria:
 
 
• Under the age of 18 years old
 
• Have not been diagnosed with PTSD or Trauma
 
• Have serious health conditions such as cancer
 
• Unable to attend 6 sessions
 

Study Product, Dose, Route, Regimen	Treatment group will receive 6 sessions, each lasting 1.5 hours of PEMF treatment over the course of 3 weeks through the CE-marked CIO devices

	classified by the U.S. Food & Drug Administration as a Type 11a Medical Device. SCIO devices contain a frequency generator and scanning technology, along with electrode harnesses that connect to the forehead, wrists, and ankles. The devices are controlled by software that is guided by A.I.
Statistical Methodology	Primary Endpoint: Symptoms of PTSD & Trauma are evaluated through a questionnaire, with scale ratings for different symptoms. Symptoms were correlated with information available on the NHS website.

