Rate The Severity of Anger or Irritable Outbursts	Average Score: 4.8
Rate How Difficult It Is To Complete Daily Tasks	Average Score: 5.8
Rate The Severity of Your Anxiety	Average Score: 6.2

Rate Your Level of Overall Happiness	Average Score: 6.2
Rate Your Level of Satisfaction and Fulfilment In Life	Average Score: 5.8

As illustrated in the above table, symptoms varied among the patients. As an overall judgement, all patients were experiencing mild to severe symptoms related to PTSD and Trauma.

It is important to note that three of the patients had received medication for their symptoms prior to the study, but none were currently receiving treatment during the clinical trial. There was an overwhelming consensus that prescription medication from the NHS was not beneficial in helping their symptoms. One patient felt 'failed' by the therapy they had received, whilst others noted that the medication exacerbated symptoms.

Regarding sleeping, the patients were given an option to describe their sleeping situations. All patients reported a problem with sleeping. These causes ranged from harmful internal dialogue and flashbacks to insomnia and difficulty gaining a restful sleep.

These initial results will be used in the 'After Trial Results' section, where the averages will be compared, and conclusion can be drawn. Further observations will be available below the initial results to accord for any individual cases requiring attention, or further clarification on certain results.

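### The closing text credits PEMF with the improvement and presents it as an alternative to medication; one uncontrolled arm of five patients supports neither conclusion

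*Combined protocol and SAP*

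**What the plan says.** The Study Summary describes the design as "Single arm observing treatment intervention; no control, no placebo/sham". Methods, Study Design, gives five subjects, all treated alike, and bases the findings on a questionnaire completed before and after. It also says "Patients were encouraged to rest and relax whilst the therapy was conducted".

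On medication, the section Prior to the Trial reports that three patients had taken it before the study and that "none were currently receiving treatment during the clinical trial". It adds: "There was an overwhelming consensus that prescription medication from the NHS was not beneficial in helping their symptoms".

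The conclusions come in the Discussion and in Reflections and Considerations with its closing text:

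- Discussion: "It is evident that the PEMF treatment is beneficial in providing patients with a relaxing and calm therapy".
- Closing text, on efficacy: "this clinical trial was a success in meeting its primary objective in improvement symptoms related to PTSD and Trauma through PEMF". It adds that the evidence in the document bears these conclusions out, and later claims significant benefits for bio-resonance treatment.
- Closing text, on medication: "The clinical trial also concludes that PEMF therapy is a beneficial, non-invasive alternative to prescription medication in relation to PTSD and Trauma".

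**The concern.** Two conclusions go beyond the data.

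**Efficacy.** A before/after change in one arm adds together everything that happened to the patients over three weeks: the device, rest, contact with staff, expectation and time. Saying that symptoms improved through PEMF assigns the whole change to one of these.

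**Medication.** The sentence is worded as something the trial concluded, and it carries no qualification of its own. A reader could take it as a tested result in a condition for which the Background lists medication among the available NHS treatments. No such test took place.

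**Working it through.** **Step 1. Do the reported changes reproduce?** Change = mean after (After The Trial) minus mean before (Prior to the Trial). Higher scores are read as better.

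| Item | Before | After | Change |
|---|---|---|---|
| Depression | 6.4 | 6.4 | 0 |
| Anxiety | 6.2 | 7 | 0.8 |
| Headaches or brain fog | 4.6 | 6 | 1.4 |
| Daily tasks | 5.8 | 7.4 | 1.6 |
| Fatigue | 5 | 6.8 | 1.8 |
| Quality of life | 6 | 8 | 2.0 |
| Happiness | 6.2 | 8.2 | 2.0 |
| Satisfaction and fulfilment | 5.8 | 7.8 | 2.0 |
| Flashbacks | 5 | 7.4 | 2.4 |
| Falling asleep | 5.6 | 8.2 | 2.6 |
| Anger | 4.8 | 7.4 | 2.6 |

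All 11 changes agree with the reported size. Ten of 11 rose: 7 of the 8 symptom items (by 0.8 to 2.6) and all 3 well-being items (by 2.0 each). The arithmetic is sound, so the question is what the changes can be attributed to.

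**Step 2. Is there anything to subtract?** Effect of PEMF = change with PEMF minus change without PEMF. The first term is in the table. The second has no source: control patients 0, sham patients 0, and no figure anywhere in the documents for change without PEMF. The difference cannot be calculated for any item.

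**Step 3. Does the document itself name other contributors?**

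- Rest: Study Design says patients were encouraged to rest. The Discussion suggests that more rest and relaxation helped patients manage negative emotions. Reflections and Considerations suggests that taking time out to attend is itself restful. The document presents this relaxation as part of PEMF or as a side effect of it, but without a sham session it cannot be told apart from relaxation due to attending and lying still.
- Talking: Reflections and Considerations says two of the five patients could explain their triggers and emotions more clearly to the practitioner. It likens this to CBT and credits voicing symptoms for their better sleep. Falling asleep is one of the two items with the largest change (2.6).
- Expectation and time: with one open arm and self-ratings, neither is controlled.

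The document therefore credits talking for part of the sleep result and then credits PEMF for the improvement as a whole, without separating the two.

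**Step 4. What medication evidence is there?** Patients on a medication comparator: 0. Patients with past medication: 3 of 5. The available text gives recalled opinion (Prior to the Trial) and one pre-trial rating of past medication with three responses (Illustrations, item 1.18). After The Trial says "patients were asked to complete the same questionnaire that was sent out prior to the clinical trial", but no medication result appears there or in the post-trial survey items 2.1 to 2.11. A repeat rating of past medication would not have been a comparison in any case.

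**The case against.** The strongest defence is that this is a small pilot that hides nothing. The design is stated, the raw means are shown, the success claim is introduced as the sponsor's opinion, the results are said not to represent the whole U.K., and a larger study with control and sham groups is recommended. All of that is true, but it does not withdraw either conclusion. The opinion label opens the closing text only; the claim of success earlier in Reflections and Considerations does not carry it. The caveat concerns who the results apply to, not what caused them. Asking for control groups next time confirms that they were absent here.

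A second defence is that an alternative may simply mean another option. This is fair: a reader might infer a claim that PEMF equals or beats medication, and the sentence does not say that. It still calls PEMF beneficial, which needs the efficacy conclusion, and it presents the statement as something the trial found.

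Some stronger readings should also be resisted:

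- *That the single arm is itself an error.* It is a disclosed choice.
- *That rest or talking explains the change and PEMF did nothing.* The documents give no figure for change without PEMF. Assuming one common background gain for all items is not informative: because depression did not change, any positive value would imply that PEMF made depression worse, and nothing in the documents supports choosing a value.
- *That only two patients talked with staff.* During The Trial records verbal feedback in sessions with each patient; the two are singled out for communicating more clearly.
- *That no patient received any treatment.* All five received PEMF. The statement about none being on treatment stands in a sentence about medication.
- *That the Discussion sentence is a general efficacy claim.* Read in full, it describes the benefit as coming through a relaxing therapy. It needs restating because that relaxation cannot be attributed to the device.

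Some sections were not available for review and may hold patient statements. They could not supply a comparator that the Study Summary and Study Design exclude.

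**Conclusion.** The concern holds. Mean self-ratings rose on 10 of 11 items, by 0.8 to 2.6 points, with depression unchanged. The part due to PEMF is not identifiable, whether it is all, some or none of the change. The medication conclusion rests on 0 comparators and on recalled experience from at most three patients. The verdict relies only on the stated design and the reported means and needs no assumed background change. It concerns the inference drawn, not the observed changes, which stand as a description of these five patients.

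**What to change.** 1. In the closing text, delete the sentence presenting PEMF as an alternative to medication, or replace it with a statement that no comparison with medication was made.
2. Restate the efficacy conclusions wherever they occur: the statement of evident benefit in the Discussion, the claim of success on the primary objective in Reflections and Considerations, and, in the closing text, the attribution of improvement to PEMF and the claim of significant bio-resonance benefits. Suggested wording:

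> In five patients with no control or sham group, mean self-ratings changed by 0 to 2.6 points on 11 items, with 10 rising. Patients were encouraged to rest during sessions and spoke with staff; at least two described their triggers and emotions to the practitioner. The effects of PEMF, rest, talking, expectation and time cannot be separated, and no comparison with medication was made.

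The table of means and the recommendation for a larger study with control and sham groups can stay. The cost is wording only, with no new data or analysis; the stated conclusion becomes less favourable.
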